5.2 Rationale for trial design

The trial is double-blinded with regards to different dose levels of once-weekly NNC0195-0092, but open labelled with regards to daily hGH as active-controlled arm. The open-label design is chosen in order to be able to compare local tolerability, (i.e. daily vs. weekly injections), which is not possible if a double-dummy design was applied. Furthermore, double-dummy design will not allow comparing patient satisfaction related to daily vs. weekly injections.

The safety extension trial period will be open labelled since only one dose level of NNC0195-0092 will be used. Additionally, in the long-term safety extension trial period, all subjects randomised to Norditropin® FlexPro® will be switched to NNC0195-0092 ([REDACTED] mg/kg/week). All subjects in cohort II and III will receive treatment with NNC0195-0092 ([REDACTED] mg/kg/week).

The trial will be observer blinded (applicable for cohort I only) with regards to primary endpoint (i.e. the person performing the height measurements will be blinded to treatment allocation). Observer blinding with regards to primary endpoint is not applicable for the long-term safety extension and any visits thereafter. GH treatment-naïve GHD pre-pubertal children is the trial target population for treatment as this is a sensitive and well-known model. The children need to be pre-pubertal to avoid interference of the pubertal growth spurt with the treatment effect. The trial will be multinational to ensure that the results are applicable for subjects with different demographic characteristics. Two additional age groups; cohort II (< 2 years and 26 weeks at screening) and cohort III (> 9 years (girls)/>10 years (boys) and ≤ 17 years at screening) are included in the long-

term safety extension trial period, based on a request from the FDA, as they may benefit from GH therapy.

The 26 week main trial period is the minimum expected time needed for evaluation of cohort I's primary endpoint (annualised HV). The 26 week extension trial period and the 104 week safety extension trial period are added primarily to collect additional safety data. The 208 week long-term safety extension trial period is added to collect data on long-term safety, as well as data on subjects reaching near adult height (NAH). The entire treatment period is 364 weeks followed by a 30 day follow up period. For cohort I subjects who continue treatment until NNC0195-0092 is available for prescription, or August 2024, at the latest, the treatment period will be longer. The follow up period is included to collect information about adverse events.

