4.1 Objectives

4.1.1 Cohort I

Primary objective:

- To evaluate the efficacy of multiple dose regimens of once-weekly NNC0195-0092 after 26 weeks of treatment in GH treatment naïve pre-pubertal children with GHD, compared to once-daily hGH administration (Norditropin® FlexPro®).

Secondary objectives:

- To evaluate the safety of multiple dose regimens of once-weekly NNC0195-0092 during 26 weeks of treatment in GH treatment naïve pre-pubertal children with GHD.
- To evaluate the efficacy and safety of multiple dose regimens of once-weekly NNC0195-0092 for up to 364 weeks of treatment in GH treatment naïve pre-pubertal children with GHD, compared to Norditropin® FlexPro®.
- To investigate the impact of NNC0195-0092 relative to Norditropin® FlexPro® on wellbeing, psychosocial functioning, treatment satisfaction and preference in GH treatment naïve pre-pubertal children with GHD by using patient reported outcome (PRO) questionnaires.
- To monitor NNC0195-0092 and Norditropin® PK throughout the trial.

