Data management is the responsibility of Novo Nordisk.

Appropriate measures, including encryption of data files containing person identifiable data, will be used to ensure confidentiality of subject data, when they are transmitted over open networks.

Data from central laboratories will be transferred electronically. In cases where data is transferred via non-secure electronic networks, data will be encrypted during transfer.

The subject and any biological material obtained from the subject will be identified by subject number and trial ID. Appropriate measures such as encryption or leaving out certain identifiers will be enforced to protect the identity of subjects in all presentations and publications as required by local, regional and national requirements.

DBLs are planned during the trial, facilitating analysis of the 26 weeks main trial period, 52 weeks extension trial period and 104 and 156 weeks safety extension trial period the 364 weeks long-term safety extension period and the 'extension until NNC0195-0092 is available for prescription for children with GHD period' data. Further interim reporting may be performed in association with marketing authorisation application or in connection with Health Authorities e.g. FDA, EMA and PDMA requirement for/during the regulatory review. The final DBL will occur after the 208 week long-term safety extension trial period (368 weeks) is completed.

16 Computerised systems

Novo Nordisk will capture and process clinical data using computerised systems that are described in Novo Nordisk Standard Operating Procedures and IT architecture documentation. The use and control of these systems are documented.

Investigators working on the trial may use their own electronic systems to capture source data.

17 Statistical considerations

If necessary, a statistical analysis plan (SAP) may be written in addition to the protocol, including a more technical and detailed elaboration of the statistical analyses. The SAP will be finalised before the first pDBL.

Biostatistics, Novo Nordisk, will be responsible for the statistical analyses.

The one-sided test used for the primary endpoint is based on an alpha level of 2.5%. All other statistical tests conducted will be two sided on the 5% significance level. Age group is defined as a factor with 2 levels: <6 years ≥ 6years. No adjustment for multiple testing will be applied.

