17.1 Sample size calculation

Sample size calculations (for cohort I) are based on an assumption of a standard deviation of 3.1 cm/year for HV after 26 weeks of treatment and the use of a delta value of -3.8 cm/year (where delta corresponds to the non-inferiority margin in a non-inferiority trial) and a one-sided significance level of 2.5%. This results in 15 subjects per treatment arm. Expecting at most 7% dropout during the trial, 15 subjects randomised per treatment arm should assure 87% power for getting a 95% confidence interval for the estimated treatment difference that lies completely above the chosen delta value when comparing a NNC0195-0092 treatment arm to the Norditropin® FlexPro® treatment arm, given that the two treatments are equal.

The addition of cohort II and III is based on a regulatory request from FDA and no formal sample size calculation was performed for these cohorts. The statistical considerations for cohort II and III can be found in section [17.3.2](#) and [17.4.3](#).

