17.4 Secondary endpoints

17.4.1 Supportive secondary efficacy endpoints (cohort I)

Changes from baseline to end of main trial period (week 26) in the following variables will be used to address the primary objective:

- Height standard deviation score (SDS)
- HV SDS
- IGF-I SDS
- IGFBP-3 SDS

Additionally, scores of the following PRO questionnaires will be used to address the secondary objective of investigating impact of NNC0195-0092 relative to Norditropin® FlexPro® on wellbeing, psychosocial functioning and treatment satisfaction in GH treatment naïve pre-pubertal children with GHD:

- Change from baseline to week 26 in TRIM-CGHD-O: Treatment Related Impact Measure – Child Growth Hormone Deficiency- Observer
- TB-CGHD-O: The Treatment Burden Measure – Child Growth Hormone Deficiency – Observer at week 26
- TB-CGHD-P: The Treatment Burden Measure – Child Growth Hormone Deficiency – Parent/Guardian at week 26

The secondary efficacy endpoints: change in height SDS, HV SDS, IGF-I SDS and IGFBP-3 SDS from baseline will be analysed using an MMRM similar to the MMRM used for the primary analysis of the primary endpoint with baseline assessment as covariate and treatment, age group, sex, region and sex by age group interaction term as factors, all nested within week as a factor. For the PRO based endpoints, this model corresponds to an analysis of variance with treatment, age group, sex, region and sex by age group interaction as factors. For change from baseline in TRIM-CGHD-O, the baseline score value is added to the model as a covariate.

Annualized HV at 39 weeks and at 52 weeks are derived analogous to the HV in the main trial period: (height at d weeks visit-height at baseline) / (time from baseline to d weeks visit in years), where d=39, 52.

Changes from baseline to end of extension trial period (week 52) in the above listed variables (except the two TB-CGHD PROs) will be used to support the secondary objective regarding evaluation of efficacy for up to 364 weeks of treatment and analysed analogously as above using an MMRM based on assessments 13, 26, 39 and 52 weeks (26 and 52 weeks for the PRO based endpoints). From the MMRM the treatment differences at Week 52 between NNC0195-0092 treatment arms and Norditropin® FlexPro® will be estimated with the corresponding 95% CI.

- HV (cm/year) at week 52

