HV and the two TB-CGHD PROs at week 52 will be analysed using an MMRM based on assessments 13, 26, 39 and 52 weeks (26 and 52 weeks for the 2 PRO based endpoints) with treatment, age group, sex, region and sex by age group interaction term as factors, all nested within week as a factor. For the analysis of HV, height at baseline will be included in the model as a covariate, also nested within week as a factor. From the MMRM the treatment differences at Week 52 between NNC0195-0092 treatment arms and Norditropin® FlexPro® will be estimated with the corresponding 95% CI.

Changes from end of main trial period (week 26) to end of extension period (week 52) in all of the above mentioned efficacy variables will also be used to support the secondary objective regarding evaluation of efficacy for up to 364 weeks of treatment and will be analysed using descriptive statistics.

- Bone age (X-Ray of left hand and wrist, central assessed according to Greulich & Pyle atlas)¹⁹ progression vs. chronological age
- Serum NNC0195-0092 concentrations and changes throughout the trial

In addition, NNC0195-0092 serum concentrations and changes during the trial and bone age progression vs. chronological age at visit (week 52) will be analysed using descriptive statistics.

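### The PRO questions are weekly versus daily, but the only contrasts planned are single dose arms against Norditropin; an averaged contrast from the same model would have two thirds of the variance

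*Combined protocol and SAP*

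**What the plan says.** Section 5.2 gives two reasons for not using a double dummy against Norditropin. One is local tolerability of daily against weekly injections. The other is that a "double-dummy design will not allow comparing patient satisfaction related to daily vs. weekly injections". The matching secondary objective in section 4.1.1 is "To investigate the impact of NNC0195-0092 relative to Norditropin® FlexPro® on wellbeing, psychosocial functioning, treatment satisfaction and preference", with no mention of dose level.

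All three NNC0195-0092 arms inject once a week, and their dose levels stay double-blinded through the main and extension periods (section 11.2).

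Section 17.4.1 covers the analysis:

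- **Week 26.** "For the PRO based endpoints, this model corresponds to an analysis of variance with treatment, age group, sex, region" and the sex-by-age-group interaction; baseline score is added for TRIM-CGHD-O. No contrast is named.
- **Week 52.** A repeated-measures model on weeks 26 and 52, from which "treatment differences at Week 52 between NNC0195-0092 treatment arms and Norditropin® FlexPro® will be estimated with the corresponding 95% CI". This applies to change in TRIM-CGHD-O and to the two treatment-burden scores, TB-CGHD-O and TB-CGHD-P.

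The introduction to section 17 adds that "All other statistical tests conducted will be two sided on the 5% significance level", with no multiplicity adjustment.

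For adverse events, including injection site reactions, section 17.4.2 plans descriptive summaries by treatment: numbers, percentages, events and rates. No between-treatment estimate is specified.

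**The concern.** The trial accepted an open-label control partly so that families' experience of weekly and daily injections could be compared. For the PROs in the randomised, dose-blinded year, the plan as written answers with three separate comparisons of about 15 children against the same 15 controls. Each is imprecise, and they can point different ways by chance. No single estimate of weekly against daily is named, although the model to be fitted already supplies one with a narrower interval.

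For injection site reactions the gap is of another kind. Daily-versus-weekly tolerability is a stated reason for the design, yet no difference or confidence interval is planned.

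**Working it through.** **1. The plan's own sizing.** Section 17.1 uses an "assumption of a standard deviation of 3.1 cm/year for HV after 26 weeks of treatment", "the use of a delta value of -3.8 cm/year", a one-sided 2.5% level, 15 randomised per arm and at most 7% dropout, so about 14 evaluable per arm (15 × 0.93 = 13.95). The comparison sized is one NNC0195-0092 arm against Norditropin.

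- SE = 3.1 × √(1/14 + 1/14) = 1.172 cm/year
- Noncentrality = 3.8 / 1.172 = 3.24, with 26 df
- Power from the noncentral t = 87.7%, against the stated 87%

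The figure reproduces. It confirms 14 evaluable per arm as a fair working number, and that precision was planned for single-dose contrasts on height velocity. Nothing was sized for the PROs.

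**2. Variance of the two contrasts.** Let n be the number per arm and work in units of the residual SD.

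- Single dose minus Norditropin: variance = 1/n + 1/n = 2/n
- Mean of three weekly arms minus Norditropin, weights (1/3, 1/3, 1/3, −1): variance = 3 × (1/9)(1/n) + 1/n = 4/(3n)
- Ratio = (4/3)/2 = 2/3, so the SE ratio is √(2/3) = 0.816

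The SE is therefore 18% smaller and the information (1/variance) 50% greater. Equivalently, one single-dose contrast carries two thirds of the information in the averaged one. The ratio does not depend on n or on the SD, provided the arms are equal in size.

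| | Single dose | Averaged |
|---|---|---|
| Variance, n = 15 | 0.133 | 0.089 |
| SE, n = 15 | 0.365 SD | 0.298 SD |
| SE, n = 14 | 0.378 SD | 0.309 SD |
| 95% half-width, n = 14 | 0.76 SD | 0.62 SD |

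The half-widths round to the same values with 52 residual df (four arm means) or 48 df (after the covariate factors).

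**3. Power, for scale only.** The documents give no SD or target difference for any PRO score, so the standardised effects below are assumptions. Two-sided 5%, 15 per arm, 56 df:

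| Assumed true difference | Single dose | Averaged |
|---|---|---|
| 0.5 SD | 27% | 38% |
| 0.8 SD | 58% | 75% |
| 1.0 SD | 77% | 91% |

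**4. Injection site reactions.** No arithmetic applies. Section 5.2 names the daily-versus-weekly comparison as a design reason, and section 17.4.2 gives descriptive tables by treatment. There is no planned contrast whose efficiency could be compared with another.

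**The case against.** This is a dose-finding trial meant to inform phase 3 dose selection (section 3.2), so per-dose contrasts are natural. TRIM-CGHD-O covers symptoms and physical health (section 8.8.1), and the doses were chosen for different IGF-I exposure (section 5.5). An average over three doses describes a regimen that no child receives. This stands for TRIM-CGHD-O: making the average its main result would be a choice of estimand. It is weaker for the two burden scores, where injection frequency is the obvious driver and is common to the three arms. The averaged contrast does not assume equal dose effects.

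It is also fair to say that little is irretrievably lost. The point estimate is the mean of the three planned differences, and with equal arms its SE is about 0.816 times theirs. What is missing is a named, reported estimate. At a modest effect such as 0.5 SD, power is low either way.

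Two stronger readings are tempting, and the documents do not support them:

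- **That a third of the information is given up for local tolerability too.** Section 17.4.2 plans no contrast for injection site reactions, so there is no inefficient one to improve. The gap is a missing comparison.
- **That weekly and daily are never compared.** In weeks 52 to 156 one weekly dose level runs against daily Norditropin (section 5.1). PROs are summarised at weeks 104 and 156, and GH-PPQ records preference at week 160 in families who switched (section 17.4.3). These analyses are descriptive, without an estimated difference or interval, but they do address the question.

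A reader might also take the week-26 arm-by-arm PRO contrast as stated. It is inferred from the treatment factor and the week-52 wording.

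**Conclusion.** The point holds for the PROs at week 52 and, by inference, at week 26. The objective and the open-label rationale ask about weekly against daily, while the plan specifies only individual arms against Norditropin. The averaged contrast from the same ANOVA or repeated-measures model has two thirds of the variance, with a half-width of 0.62 rather than 0.76 SD at 14 per arm.

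This assumes equal arms and a common residual variance. Children who stop trial product no longer complete the burden questionnaires (section 8.3.3), so actual numbers may be lower and uneven. Power figures are illustrative only.

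For injection site reactions the conclusion is narrower: a comparison used to justify the design has no planned estimate.

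Section 17 allows for a separate, more detailed SAP; no such additional text is in the document reviewed. These are supportive endpoints and the primary analysis is unaffected. The change is worth considering, and arguably should be made because it is so cheap.

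**What to change.** **Section 17.4.1.** At weeks 26 and 52, add the equally weighted mean of the three NNC0195-0092 arms minus Norditropin, with 95% CI, from the models already planned.

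- For TB-CGHD-O and TB-CGHD-P, name it the main weekly-versus-daily estimate.
- For change in TRIM-CGHD-O, report it alongside the per-dose contrasts.
- Keep all per-dose contrasts, and state the week-26 contrasts explicitly.

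Section 3.1.6 describes the main period as completed, and section 5.5 has the sponsor unblinded after that database lock. Label the averaged contrast post hoc for any period already unblinded.

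**Section 17.4.2.** For injection site reactions, add an all-NNC0195-0092 column and the weekly-minus-daily difference in the proportion of children affected, with 95% CI, for weeks 0 to 26 and 0 to 52.

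**Cost.** One extra contrast per PRO model, one table column and one risk difference per period, with no new data. The drawback is that an average can hide dose dependence, which is why the per-dose results stay.

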5.3 Treatment of subjects

In the main trial period of the study subjects enrolled in cohort I will be randomised in a 1:1:1:1 manner to receive either NNC0195-0092 (approximately 45 subjects) or Norditropin® FlexPro® (approximately 15 subjects).

- NNC0195-0092: [REDACTED] mg/kg/week
- NNC0195-0092: [REDACTED] mg/kg/week
- NNC0195-0092: [REDACTED] mg/kg/week
- Norditropin® FlexPro®: [REDACTED] mg/kg/day

When the subjects have completed the main trial period (week 26) and extension trial period (week 52), all subjects initially randomised to NNC0195-0092 will be allocated to open labelled NNC0195-0092 ([REDACTED] mg/kg/week). Subjects randomised to Norditropin® FlexPro® will continue the treatment with Norditropin® FlexPro® ([REDACTED] mg/kg/day) until week 156, when they will be switched to NNC0195-0092 ([REDACTED] mg/kg/week).

After completion of the long-term safety extension (364 weeks), cohort I subjects in countries where NNC0195-0092 is not available for prescription will be offered to continue the trial and receive treatment with NNC0195-0092, [REDACTED] mg/kg/week until NNC0195-0092 becomes available for prescription in the subject's respective country or until August 2024 (expected last end-of-treatment visit for cohort I) at the latest. Novo Nordisk will inform the sites when NNC0195-0092 is considered available for prescription for children with GHD in the respective countries. However, if the health authorities in the subject's country reject the marketing application, treatment with NNC0195-0092 will be stopped for the relevant subjects. If NNC0195-0092 is not approved and commercially available in the country treatment will continue until August 2024.

Subjects who remain on treatment in the extension period after completion of the long-term safety extension (364 weeks) should attend site visits according to the flowchart in [Table 2-4](#). When NNC0195-0092 becomes available for prescription in a country, the treatment for subjects in that country will be discontinued, and end-of-treatment visit (visit 38) should be performed. The follow-up visit will take place 30 days after last treatment in the trial.

For the long-term safety extension period of the trial additional subjects will be enrolled (cohort II and III) and will be treated with [REDACTED] mg/kg/week NNC0195-0092.

Subjects in the weekly and daily dosing arms will be trained by the site staff in the use of the pen-injector and how to inject themselves with the trial drug. The first dose will be administered by the subject (at visit 2) under supervision of the site staff (Sections [2](#) and [8.10](#)). The subsequent doses will be administered by the subject at home. The subject will be instructed to inject themselves in the thighs, dorsogluteal region (upper buttocks), upper outer triceps area (back of upper arm) or in the abdomen with rotation within these body areas for each injection. Body weight will be measured at all visits during the treatment period and will be used for dosing calculation. The maximum treatment duration for a single subject is 364 weeks. No maximum calculated dose is specified.

Subjects with body weight above 50 kilograms (110 pounds) who are randomised to NNC0195-0092 will need to have two injections at dosing due to the injection pen limitations. The volume of the injections should be equal, and the injection sites should be different.

Time of injections:

- Applicable for cohort I until visit 15: NNC0195-0092 should be injected in the morning no later than 10 AM to ensure consistency of PK/PD with previous trials. The trial drug can be injected by 12 PM (noon) on the clinic visit days. Trial drug must not be administered in the morning before relevant visit procedures have been performed (Sections [8.7.6](#) and [8.7.8](#)). If a subject forgets to inject the dose in the morning, the subject must take the dose as soon as possible during the same day.
- Applicable for cohort I subjects after visit 15: NNC0195-0092 can be injected anytime during the dosing day.
- Applicable for cohort II and III: NNC0195-0092 can be injected anytime during the dosing day.
- Injections with NNC0195-0092 the day before blood sampling for anti-NNC0195-0092 antibodies must occur at least 12 hours prior to planned blood sampling.
- If the dose is not administered on the planned dosing day, the dose must then be administered as soon as possible after the missed planned dosing day.
- If the dose cannot be administered within 2 days after the planned dosing day, the dose should be skipped. The next dose afterwards should be taken on the originally planned weekday compared to baseline (randomisation).
- Subjects randomised to Norditropin® FlexPro® should inject s.c. daily in the evening (to reflect standard treatment practice) throughout the trial. Injections with Norditropin® FlexPro® the night before blood sampling for anti-hGH antibodies must occur at least 12 hours prior to planned blood sampling.
- If a subject randomised to Norditropin® FlexPro® forgets or is unable to inject the dose in the evening, the dose should be skipped. The subject should continue on the next evening with the next scheduled dose.

